4.1 Included Population

The “All Included Patients” dataset, defined as all patients accepted by the sponsor to take part in the trial, will be used for the descriptive analyses of disposition of patients in each cohort of advanced solid tumors.

4.2 Efficacy Populations

In all cohorts but SCLC, the “All Evaluable Patients” analysis set will be used for the primary endpoint analysis of ORR and for the secondary endpoints of DR, Clinical benefit (ORR or SD \geq 4 months), PFS (including PFS4/PFS6 months), and OS6/OS12 months in each cohort of advanced solid tumors. The “All Treated Patients” analysis set will also be used for the sensitivity analyses.

In SCLC cohort, the “All Treated Patients” analysis set will be used for the primary endpoint analysis of ORR and for the secondary endpoints of DR, Clinical benefit (ORR or SD \geq 4 months), PFS (including PFS4/PFS6 months), and OS6/OS12 months in each cohort of advanced solid tumors. The “All Evaluable Patients” analysis set will also be used for the sensitivity analyses.

The “All Responding Patients” set will be used for the secondary endpoint analysis of DR.

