2 STUDY DESIGN

Multicenter, open-label, exploratory, phase II clinical trial to evaluate the efficacy and safety of PM01183 in previously treated patients with the following advanced solid tumors: SCLC, H&N, NETs, biliary tract carcinoma, endometrial carcinoma, BRCA 1/2-associated MBC, carcinoma of unknown primary site, GCTs, and EFTs.

Patients with each of the aforementioned tumors will be enrolled in nine cohorts. Up to 25 evaluable patients are planned to be enrolled in each cohort (50 in the endometrial carcinoma and 100 in the SCLC cohort). To consider that PM01183 has antitumor activity in any of the tumor types analyzed, at least two confirmed responses [complete (CR) or partial response (PR)] per RECIST v.1.1 out of the 25 patients of each cohort are expected.

- If no confirmed responses are observed in the first 15 evaluable patients of each cohort, the recruitment of the corresponding cohort will be stopped.
- If one confirmed response is observed in the first 15 evaluable patients of each cohort, the recruitment of this cohort will continue to up to 25 evaluable patients.
 - In the cohort of endometrial carcinoma, if ≥ 2 confirmed responses occur in the first 25 evaluable patients, the sample size will be doubled to 50 evaluable patients.
 - In the cohort of SCLC, if ≥ 2 confirmed responses occur in the first 25 evaluable patients, the sample size will be increased to 100 evaluable patients.
- If two confirmed responses are observed in the first 15 evaluable patients of each cohort, the recruitment of the corresponding cohort can be stopped.

Only in the SCLC cohort, an IRC will be performed on all images collected and will provide a radiographic response at each time point termed. These data and the clinical database information will be used to derive the independent review efficacy information following the RECIST v.1.1. Operational details for the IRC and the algorithm and its validation by an expert panel is described in detail in the IRC charter.

In addition, for safety reasons:

- If two patients have a treatment-related death in a cohort, the recruitment of the corresponding cohort will be stopped.
- If six patients have treatment-related deaths in the whole population, the study will be stopped.

Finally,

- A determined cohort can be early closed by the Sponsor in case of a low recruitment rate.

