4 PATIENTS EVALUABILITY CRITERIA

The study population will include the following analysis sets definitions:

- “All Included Patients” analysis set is defined as all patients recorded in the database who have been included in the trial, regardless of whether they have received the study drug or not.
- “All Treated Patients” analysis set is defined as all included patients who have received any partial or complete infusion of PM01183.
- “All Evaluable Patients” analysis set is defined as all eligible patients, defined as patients accepted by the sponsor to take part in the trial, who have had at least one complete infusion of PM01183, and either have had at least one assessment (as per RECIST v1.1) or have been categorized as “treatment failures”. Patients who discontinue treatment due to any treatment-related toxicity before an appropriate tumor assessment has been performed or those who experience early death due to malignant disease or those with treatment withdrawn due to clinical PD/symptomatic deterioration with no tumor assessments will be defined as “treatment failures”. These patients will be included as non-evaluable for response in the analysis of objective response as per RECIST v1.1, although they will not be replaced as will be considered evaluable for efficacy. For the IRC assessment in SCLC patients same definition will be followed but based on its assessment.
- “All Responding Patients” analysis set is defined as all evaluable patients who have had a confirmed CR or PR as overall best response according to the RECIST v1.1. For the IRC assessment in SCLC patients same definition will be followed but based on its assessment.

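### Main PFS and OS analyses in the eight non-SCLC cohorts use a set whose membership is partly fixed after dosing; All Treated should be the main set, as in SCLC

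*SAP*

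**What the plan says.** SAP 2 states: "Patients with each of the aforementioned tumors will be enrolled in nine cohorts". Eight of the nine are therefore not SCLC. For those eight, SAP 4.2 says that the All Evaluable "analysis set will be used for the primary endpoint analysis of ORR and for the secondary endpoints of DR", and the sentence ends with "PFS (including PFS4/PFS6 months), and OS6/OS12 months in each cohort of advanced solid tumors". It names OS6/OS12 but not OS itself; SAP 11.3 covers OS, because it puts the efficacy analysis in general on All Evaluable. For SCLC, SAP 4.2 assigns the same endpoints to All Treated.

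SAP 4 defines the two sets:

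- All Treated: "all included patients who have received any partial or complete infusion of PM01183".
- All Evaluable: eligible patients "who have had at least one complete infusion of PM01183, and either have had at least one assessment" by RECIST or been classed as treatment failures.

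Three groups count as treatment failures and so stay in All Evaluable. The first is "Patients who discontinue treatment due to any treatment-related toxicity before an appropriate tumor assessment has been performed". The other two are "those who experience early death due to malignant disease or those with treatment withdrawn due to clinical PD/symptomatic deterioration with no tumor assessments".

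SAP 6.1 starts both PFS and OS at the start of treatment. SAP 4.2 and 6.1 plan a sensitivity analysis in All Treated for the non-SCLC cohorts, and 6.1 lists PFS and OS among its endpoints.

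**The concern.** A time-to-event analysis that starts at first dose should include patients on what is known at first dose. All Evaluable does not. Whether a treated patient belongs to it depends on whether a scan followed or, failing that, on why none did. The first scan is due after two three-week cycles, about six weeks in (Protocol 6.3 and 7.1).

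For ORR the restriction has a measurement rationale, and Protocol 7.1 defines ORR in evaluable patients. Protocol 3.2 attaches no such condition to PFS or OS, and OS needs no scan at all.

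The treated patients left out of the main survival estimates are:

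- those who never had a complete infusion. This condition also binds treatment failures, so a patient stopped during the first infusion for drug toxicity is a treatment failure under Protocol 5.3 but falls outside All Evaluable under SAP 4;
- those with no scan for any other reason, such as early death from a cause other than the malignancy or the drug, refusal, or an unrelated adverse event. SAP Tables 10.2.1 and 12.3.2.1 provide for such reasons.

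At stake is whether the main PFS and OS estimates describe everyone who was dosed.

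**Working it through.** The plan gives no PFS or OS target, no expected number of non-evaluable patients and no event count, so there is no figure of its own to reproduce. What can be calculated is how far a landmark estimate moves under stated assumptions.

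**Inputs.** n = 25 evaluable patients (SAP 5.1). This is a target for evaluable patients, and non-evaluable ones are replaced (Protocol 5.3), so excluded patients come on top of the 25. Assumed: m = 1 or 2 excluded treated patients; landmark survival S_eval in All Evaluable of 50%, with 30% and 70% as a range; landmark survival S_x among the excluded from 0 to 100%.

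**Formula.**

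S_treated = (n × S_eval + m × S_x) / (n + m)

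Shift = S_eval − S_treated = [m / (n + m)] × (S_eval − S_x)

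**All excluded patients die before the landmark (S_x = 0), S_eval = 50%.**

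- m = 1: S_treated = 12.5/26 = 48.1%; All Evaluable is 1.9 points higher.
- m = 2: S_treated = 12.5/27 = 46.3%; All Evaluable is 3.7 points higher.

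**Other values**, shift in points (a plus sign means that All Evaluable reads higher):

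| S_eval | m | S_x = 0 | S_x = 50% | S_x = 100% |
|---|---|---|---|---|
| 30% | 1 | +1.2 | −0.8 | −2.7 |
| 30% | 2 | +2.2 | −1.5 | −5.2 |
| 50% | 1 | +1.9 | 0.0 | −1.9 |
| 50% | 2 | +3.7 | 0.0 | −3.7 |
| 70% | 1 | +2.7 | +0.8 | −1.2 |
| 70% | 2 | +5.2 | +1.5 | −2.2 |

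With 50 evaluable patients (the endometrial target) and S_eval = 50%, one or two excluded early deaths give +1.0 or +1.9 points.

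**Kaplan-Meier check.** Take a constructed cohort of 25 with a six-month estimate of 48.0% (12/25) and add three excluded patients, a count chosen only to make the direction visible:

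- all three die early: 12/28 = 42.9%, so All Evaluable reads 5.1 points higher;
- all three are censored on day 1: they leave the risk set before any event, and the estimate stays at 48.0%;
- all three are alive at 12 months: 15/28 = 53.6%, so All Evaluable reads 5.6 points lower.

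The sign therefore depends on what happens to the excluded patients, which the documents cannot tell us in advance.

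**The case against.** The strongest reply is that the plan already covers this. An All Treated analysis of PFS and OS is pre-specified for these cohorts, so the question is only which of two planned analyses is called the main one. Listings 10.1.4 and 16.2.3 will show each non-evaluable patient with the reason. PFS and OS are secondary, descriptive Kaplan-Meier summaries in an exploratory trial (SAP 2 and 6.2), and no decision rule depends on them. At 25 patients and 50% survival, the 95% half-width is roughly 1.96 × √(0.5 × 0.5/25) = 20 points, far more than any shift above. All of this stands, and it keeps the point small. It does not supply a reason for preferring, as the main survival estimate, the set that depends on later events. The labelling is also loose: Tables 11.3.2.4 and 11.3.2.5 name no set and have no All Treated counterpart, whereas the SCLC tables 11.3.3.11 and 11.3.3.12 state theirs.

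A reader might draw three stronger conclusions that the documents do not support:

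- **That non-SCLC survival will be biased upward.** The direction is not established. Upward bias needs excluded patients who do worse than the rest, and neither their number nor their outcome is in the documents.
- **That early failures are removed.** Most of the groups expected to do badly (treatment-related toxicity stops, early malignant deaths, clinical progression without a scan) are kept, provided that they had a complete infusion. Protocol 5.8 also asks for a scan at end of treatment when none has been done and the reason for stopping is not progression, which should reduce the number never scanned.
- **That SCLC survival cannot be set beside the other cohorts.** Both sets are planned on both sides, so a like-for-like reading is available on either.

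**Conclusion.** The point holds as a choice of main analysis set, not as a demonstrated bias. In the eight non-SCLC cohorts, the main PFS and OS estimates depend partly on events after the clock starts, and for OS no measurement need justifies that. The possible distortion is modest: about 2 to 4 points upward at a 50% landmark if one or two excluded patients die early beside 25 evaluable ones, zero if they are censored at once, and of the opposite sign if they survive longer. The counts and outcomes are assumptions. With the sensitivity analysis already planned, this is an inexpensive improvement rather than a fault that threatens the trial's conclusions.

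**What to change.** In SAP 4.2, 6.1 and 11.3, make All Treated the main set for PFS, PFS4/6, OS and OS6/12 in every cohort, matching SCLC, and make All Evaluable the sensitivity set. Keep ORR on All Evaluable in the non-SCLC cohorts. State the analysis set in the titles of Tables 11.3.2.4 and 11.3.2.5.

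Both analyses are already planned, so no new data or methods are needed. There are two costs. PFS and OS may look slightly shorter, and within a cohort their denominator will differ from that of ORR, which a table footnote should explain. In return, the survival tables will share a denominator with the baseline tables, which SAP 11.1 already places on All Treated.

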4.3 Safety Population

The safety analysis will be based on the “All Treated Patients” analysis set by cohort of tumor types and total population.

Based on the newly available information, additional patients will be recruited to test the null hypothesis that 10% or less patients get a response ($p \leq 0.10$) versus the alternative hypothesis that 25% or more patients get a response ($p \geq 0.25$). The variance of the standardized test is based on the null hypothesis. The type I error (alpha) associated with this one-sided test is 0.025 and the type II error (beta) is 0.144 (normal approximation; ~ 0.16 if exact binomial distribution); hence, statistical power is $\sim 86\%$ (normal approximation; $\sim 84\%$ if exact binomial distribution). With these assumptions, if the number of patients who achieve a confirmed response is ≥ 10 , then this would allow the rejection of the null hypothesis.

With the sample size of 100 and 50 evaluable patients in each indication (SCLC and endometrial), the obtained confidence interval will be narrower and its half-width will be confined to $\pm 15\%$.

6 STATISTICAL METHODOLOGY FOR EFFICACY

Frequency tables will be prepared for categorical variables, whereas continuous variables will be described by means of summary tables that will include the median, mean, standard deviation, minimum, and maximum of each variable.

6.1 *Planned Analyses and Definitions*

Primary Endpoint

The primary study analysis except for SCLC cohort will be based on the ORR in the "All Evaluable Patients" population set. For SCLC cohort, the primary study analysis will be based on the ORR in the "All Treated Patients" population set.

Overall response rate (ORR) is calculated as the number of patients who have had a confirmed CR or PR as overall best response according to the RECIST v1.1, divided by the number of patients in the "All Evaluable Patients" ("All Treated Patients" in SCLC cohort) population set.

Secondary Endpoints

The following time-related parameters will be analyzed according to available follow-up data:

Duration of response (DR) is defined as the time from the first observation of response to the date of disease progression, recurrence or death. Other cases will be censored. Although the responses have to be confirmed according to RECIST v1.1, the first documentation (not the confirmation) will be taken into account to calculate DR. Patients who progress or die will be considered to have had an event,

except if this event occurs after the start of subsequent antitumor therapy, in which case the patient will be censored at the time of last disease assessment prior to or on the first day of the first subsequent antitumor therapy.

Clinical benefit rate is calculated as the number of patients who have had a confirmed CR, PR, or SD ≥ 4 months as overall best response according to the RECIST v1.1, divided by the number of patients in the “All Evaluable Patients” (“All Treated Patients” in SCLC cohort) analysis set.

Progression-free survival (PFS) is defined as the time from the date of start of treatment to the date of documented progressive disease (PD) by RECIST v1.1 or death (regardless of the cause of death), whichever comes first. Patients who progress or die will be considered to have had an event of progression, except if this event occurs after the start of subsequent antitumor therapy, in which case the patient will be censored at the time of last disease assessment prior to or on the first day of the first subsequent antitumor therapy. If the patient is lost for the assessment of progression during the follow-up period, or has more than one missing follow-up between the date of last tumor assessment and the date of progression, death or further antitumor therapy, the PFS/DR will be censored at the date of last valid disease assessment before the missing evaluations.

The date of response, the date of radiological progression, according to the investigator assessment and the independent assessment by IRC when applicable (i.e., SCLC cohort), the date of clinical PD and the date of death will be registered and documented, as appropriate.

Overall survival (OS) is defined as the time from the date of start of treatment to the date of death or last contact. **One year (1y-OS)/6 months overall survival** is defined as the Kaplan-Meier estimate of the probability of patients being alive at 12/6 months after the date of start of treatment.

A sensitivity analysis for all cohorts but SCLC will be performed for ORR, Clinical Benefit Rate, PFS and OS in the “All Treated Patients population”. For the SCLC cohort, the sensitivity analysis will be carried out the “All Evaluable Patients”.

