3.2 SECONDARY ENDPOINTS

Efficacy (all cohorts):

- **Duration of Response (DR) by IA**, defined as the time between the date when the response criteria (PR or CR, whichever one is first reached) are fulfilled to the first date when disease progression (PD), recurrence or death is documented.
- **Clinical Benefit by IA**, defined as ORR or SD lasting over four months (SD \geq 4 months).
- **Progression-free Survival (PFS) by IA**, defined as the period of time from the date of first infusion to the date of PD, death (of any cause), or last tumor evaluation.
- **PFS4/PFS6 by IA**, defined as the Kaplan-Meier estimates of the probability of being free from progression and death after the first infusion at these time points (4 and 6 months).
- **OS**, defined as the period of time from the date of first infusion to the date of death or last contact in case of patients lost to follow-up or alive at the clinical cut-off established for the cohort.
- **OS6/OS12**, defined as the Kaplan-Meier estimates of the probability of being alive after the first infusion at these time points (6 and 12 months).

Efficacy (only in the SCLC cohort):

- **ORR, Clinical Benefit, DR, PFS and PFS4/PFS6 by IRC**. The same definitions detailed for IA will be used.

Plasma Pharmacokinetics (PK) of PM01183

- **Non-compartmental (NCA) PK parameters**: area under the curve (AUC), maximum plasma concentration (C_{max}), clearance (CL) and half-life ($t_{1/2}$). **Population PK parameters** of the compartment model to be developed (initially based on Volumes and Clearance), and **PK/PD correlation parameters**, if applicable.

Pharmacogenetics:

- This analysis will be performed in those patients who signed the written informed consent (IC) for the pharmacogenetic sub-study. The presence or absence of known polymorphisms from a single sample collected at any time during the study, but preferably just before treatment start in Cycle 1, will be assessed to explain the individual variability in the main PK parameters.

Pharmacogenomics (PGx):

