7. STUDY EVALUATIONS

7.1 EFFICACY

The primary objective of this study is to assess the antitumor activity of PM01183 in terms of **overall response rate (ORR)**, primary endpoint, supported by the secondary endpoint duration of response (DR), both assessed by the IA.

ORR will be assessed using the RECIST v.1.1 (see [APPENDIX 4](#)) on a set of measurable lesions identified at baseline as target lesions or as non-target lesions (if any), and followed until disease progression (PD) by an appropriate method (e.g., helical CT-scan, MRI).

Radiological tumor assessment will be performed at baseline, and every two cycles from the onset of the study treatment until Cycle 6 or evidence of PD. After Cycle 6, tumor assessment will be performed every three cycles until evidence of PD. If an objective response is observed, according to the RECIST v1.1, it must be confirmed by the same method at least four weeks after the date of the first documentation of response.

ORR is defined as the percentage of evaluable patients with a confirmed response, either complete (CR) or partial response (PR), from the start of treatment to the date of progression or the start of a subsequent therapy or end of patient's follow-up, according to the RECIST (v. 1.1).

DR will be calculated from the date of first documentation of response to the date of first documented PD, recurrence or death due to any cause in the responder patients.

The date of response, the date of radiological or clinical PD, according to the investigator assessment and the independent assessment by IRC when applicable (i.e., SCLC cohort), and the date of death will be registered and documented, as appropriate.

A copy of CT-scans or MRIs can be requested by the Sponsor in selected cases.

In SCLC patients, anonymized copies of all the images obtained throughout the study must be submitted to the Sponsor. These copies of CT scans, MRIs and any other documented methods to evaluate tumor response or progression in the SCLC cohort should be available for external radiological review by an IRC. The IRC will determine the patient's best response and assign the date of first documentation of response and progression/censoring according to RECIST v.1.1.

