(*) Confirmed CR + PR. Binomial exact estimator and 95% CI.

Table 11.3.3.30 DR by IA and IRC excluding CTFI < 30.

	IA	IRC
N		
Events		
Censored		

Median DR		
DR at 4 months		
DR at 6 months		
DR at 12 months		

Kaplan-Meier plot will also be shown (Figure 11.3.3.30.1 DR by IA excluding CTFI<30 (All treated patients), Figure 11.3.3.30.2 DR by IRC excluding CTFI<30 (All treated patients) and 11.3.3.30.3 DR by IA and IRC excluding CTFI<30 (All treated patients))

Table 11.3.3.31 Clinical benefit rate and Disease control rate by IA and IRC excluding CTFI<30 (All treated patients).

		Percentage	Lower 95% limit	Upper 95% limit
IA	Clinical benefit rate*			
	Disease control rate**			
IRC	Clinical benefit rate*			
	Disease control rate**			

(*) CR + PR + SD \geq 4 months. Binomial exact estimator and 95% CI.

(**) CR + PR + SD. Binomial exact estimator and 95% CI.

Table 11.3.3.32 PFS IA and IRC excluding CTFI<30 (All treated patients).

	IA	IRC
N		
Events		
Censored		
Median PFS		
PFS at 4 months		
PFS at 6 months		
PFS at 12 months		

Kaplan-Meier plot will also be shown (Figure 11.3.3.32.1 PFS by IA excluding CTFI<30 (All treated patients), Figure 11.3.3.32.2 PFS by IRC excluding CTFI<30 (All treated patients) and Figure 11.3.3.32.3 PFS by IA and IRC excluding CTFI<30 (All treated patients))

Table 11.3.3.33 OS excluding CTFI<30 (All treated patients).

	OS
N	
Events	
Censored	
Median OS	
OS at 6 months	
OS at 12 months	
OS at 24 months	

Kaplan-Meier plot will also be shown (Figure 11.3.3.33).

DR and PFS considering event in the clinical progressions:

Table 11.3.3.34 DR IA giving event in clinical PD (All treated patients).

	DR
N	
Events	
Censored	
Median DR	
DR at 4 months	
DR at 6 months	
DR at 12 months	

Kaplan-Meier plot will also be shown (Figure 11.3.3.34).

Table 11.3.3.35 PFS IA giving event in clinical PD (All treated patients).

	PFS
N	
Events	
Censored	
Median PFS	
PFS at 4 months	
PFS at 6 months	
PFS at 12 months	

Kaplan-Meier plot will also be shown (Figure 11.3.3.35).

Survival in responders:

Table 11.3.3.36 OS in responders by IA and by CTFI (All treated patients).

	CTFI < 90 days*			CTFI ≥ 90 days*			Total***
	R**	RR**	Total*	S**	VS**	Total*	
N							
Events							
Censored							
Median OS							
OS at 6 months							
OS at 12 months							
OS at 24 months							

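### Outside the SCLC cohort the plan never tests PFS with unscanned clinical progression counted as an event, so PFS4 and PFS6 can read too high where such patients occur

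*SAP*

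**What the plan says.** **PFS event.** SAP 6.1 measures PFS from the start of treatment to "documented progressive disease (PD) by RECIST v1.1 or death (regardless of the cause of death), whichever comes first". Protocol 3.2 is wider: the period runs "from the date of first infusion to the date of PD, death (of any cause), or last tumor evaluation", with no RECIST limit on PD.

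**PFS censoring.** If the event falls after a new antitumor therapy has begun, SAP 6.1 has the patient "censored at the time of last disease assessment prior to or on the first day of the first subsequent antitumor therapy". If at least two follow-ups are missed before progression, death or new therapy, PFS is cut back to the last valid assessment before the gap.

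**Clinical progression is recorded.** Protocol 7.1 requires documentation of "The date of response, the date of radiological or clinical PD". SAP 6.1 likewise has the clinical PD date recorded. Neither limits this to SCLC.

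**ORR.** SAP 4 counts as treatment failures "those with treatment withdrawn due to clinical PD/symptomatic deterioration with no tumor assessments". It adds: "These patients will be included as non-evaluable for response in the analysis of objective response as per RECIST v1.1". They stay in the ORR denominator as non-responders.

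**Analysis with clinical PD as an event.** SAP 8.11 and 11.3 plan this for SCLC only. The outputs are Tables 11.3.3.34 (DR) and 11.3.3.35 (PFS), both by investigator assessment. The other eight cohorts have PFS Table 11.3.2.4 and, under SAP 6.1, a repeat in All Treated Patients.

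**The concern.** A patient who stops because of clinical worsening leaves the PFS risk set for a reason tied to the outcome, so the censoring is informative.

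Later documentation is unlikely. Protocol 5.8 asks for an end-of-treatment scan only if treatment stopped for a reason other than PD, and Protocol 5.9 gives follow-up scans only to patients who stopped without PD. The SAP expects such patients in any cohort: the footnote to Table 10.1.1 includes early PD without imaging among the patients evaluable for efficacy, and does not limit this to SCLC.

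At stake is how far the PFS4 and PFS6 reported for eight cohorts depend on a rule whose effect the planned outputs do not show.

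**Working it through.** The plan states no PFS assumption, event count or power, so there is no figure to reproduce. The check is of the rules first, then of the possible size.

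**1. What happens to a patient with unscanned clinical PD**

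| Later course | PFS under SAP 6.1 | PFS with clinical PD counted |
|---|---|---|
| New therapy starts | Censored at last scan, or baseline if none | Event at clinical PD |
| At least two follow-ups missed | Censored at last scan before the gap | Event at clinical PD |
| Death, no new therapy, at most one follow-up missed | Event at death | Event at clinical PD, which is earlier |

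Rows 1 and 2 are informative censoring and row 3 delays the event. All three push the PFS estimate up.

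**2. Does any planned output test this outside SCLC?** The All Treated repeat changes who is analysed, not what counts as an event. OS does not use progression. The table of censoring reasons (11.3.3.17) is also SCLC-only. The other exploratory analyses allowed by SAP 8.11 are not pre-specified.

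**3. Limiting case.** Assume exponential PFS with a 3.5-month median, so S(t) = exp(−ln2 × t/3.5), giving S(4) = 0.453 and S(6) = 0.305. Let a share f of all patients progress clinically before the first scan, all censored at time zero. Kaplan-Meier then estimates S/(1−f).

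- f = 10%: PFS4 0.453/0.90 = 0.503, PFS6 0.305/0.90 = 0.339 (up 5.0 and 3.4 points).
- f = 15%: PFS4 0.453/0.85 = 0.533, PFS6 0.305/0.85 = 0.359 (up 8.0 and 5.4 points).

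The first scan is due after two cycles, about 1.38 months. In this model 1 − exp(−ln2 × 1.38/3.5) = 23.9% of patients fail before then. So f = 10% makes 0.10/0.239 = 42% of those early failures unscanned clinical PD with no counted death, and f = 15% makes it 63%. Nothing in the documents supports shares that high.

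**4. Simulation with the SAP 6.1 rules.** Assumed: exponential progression with a 3-month median; scans every six weeks throughout; radiological PD dated at the next scan; f now the share of progressions, at any time, that are clinical and unscanned. Each f was run with three pairs of inputs: mean time from clinical PD to death 1, 2 or 3 months, with 0%, 30% or 50% starting new therapy. A death counted unless new therapy had started or more than one scheduled scan had passed. There were 300,000 simulated patients per scenario.

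| f | PFS4 (%), PD counted → SAP rule | Rise (points) | PFS6 (%), PD counted → SAP rule | Rise (points) |
|---|---|---|---|---|
| 5% | 52.1–52.3 → 52.7–54.0 | 0.6–1.7 | 27.7–27.9 → 28.2–29.2 | 0.4–1.3 |
| 10% | 51.5–51.6 → 52.6–55.0 | 1.1–3.4 | 27.6–27.8 → 28.6–30.4 | 0.8–2.8 |
| 20% | 50.2–50.3 → 52.5–57.2 | 2.3–7.0 | 27.3–27.4 → 29.0–33.2 | 1.7–5.9 |
| 30% | 48.7–49.0 → 52.1–59.6 | 3.4–10.6 | 26.9–27.2 → 29.4–36.3 | 2.4–9.1 |

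The SAP rule gave the higher value in all 12 scenarios. Its median was 4.14 months throughout, which is the third scan date (3 × 1.38). With clinical PD counted, the median was 4.10–4.14 months for f up to 20% and 3.57–3.66 months at 30%.

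Steps 3 and 4 use different medians and define f differently, so compare the shifts, not the levels.

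**The case against.** The strongest reply is that this is small and decides nothing. In these cohorts PFS is secondary and untested in an exploratory single-arm trial, and activity is judged on ORR. Seven of the eight cohorts plan at most 25 evaluable patients, so an approximate 95% interval around a PFS4 of 45% is ±1.96 × √(0.45 × 0.55/25), about ±20 points. A shift of 1 to 5 points lies well inside that. Concentrating sensitivity work on the 100-patient cohort with independent review is proportionate. Every cohort also gets discontinuation reasons, counts inevaluable for response, PFS event and censoring counts, and OS.

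Most of this stands, and it limits the weight of the point. It does not remove it: none of those outputs changes the event definition, and the interval measures sampling error, not a one-directional bias.

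A reader might infer more than the documents support:

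- **That PFS is biased in all eight cohorts.** No document gives a count of unscanned clinical PD. A cohort with none has no bias from this source.
- **That the bias is 5 to 8 points on PFS4.** That needs every such patient censored at time zero, whereas SAP 6.1 still counts many later deaths.
- **That a failure for ORR who is censored for PFS is a contradiction.** A response proportion and a censored time treat the same patient differently without conflict. The automatic ORR rule also covers only patients with no tumor assessment; clinical PD after an earlier scan is classed by best response.
- **That DR suffers in the same way.** Responders have scans, so censoring at time zero cannot arise. A responder with later unscanned clinical PD can still be censored at the last scan, which is why Table 11.3.3.34 has a use.

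**Conclusion.** The point holds in conditional form. Where patients have clinical PD without a scan, the SAP rule raises PFS4 and PFS6, and outside SCLC no planned output shows by how much.

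The size cannot be known from the documents. Under the simulation's assumptions it is about 1 to 3 points on PFS4 if 10% of progressions are of this kind, and under 2 points at 5%. The 5-point figure at 10% is an upper limit for patients who progress clinically before the first scan. Both results assume that scans not done after withdrawal count as missed; the SAP does not say whether scans that were never scheduled do. The median may move little, because it falls on the scan grid.

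The ORR decision rules are unaffected. The SAP's RECIST-only event is narrower than the protocol's definition of PFS, and the two should agree. This is a worthwhile addition to secondary analyses, not a threat to the trial's conclusions on activity.

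**What to change.** For each non-SCLC cohort, add to SAP 11.3.2:

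- a PFS table by investigator assessment with clinical PD as an event, matching Table 11.3.3.35;
- a table of censoring reasons, matching Table 11.3.3.17;
- where the cohort has responders, the DR version, matching Table 11.3.3.34.

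Keep RECIST-only PFS as the main analysis, and bring the PFS wording of SAP 6.1 and Protocol 3.2 into line.

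The cost is some extra tables from analyses already specified for SCLC, run on data already collected. PFS in the added tables may look slightly shorter.
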